## **11.0 Safety Analysis**

### **11.1 General Considerations**

All subjects who receive at least one dose of study drug will be included in the safety analyses. Safety data will be summarized only for the overall treatment cohort and not by prior treatment.

### **11.2 Analysis of Adverse Events**

#### **11.2.1 Treatment-Emergent Adverse Events**

Unless otherwise specified, summaries of adverse events will include adverse events that are treatment-emergent relative to dosing of the DAAs. Treatment-emergent adverse events are defined as any event that begins or worsens in severity after initiation of study

drug through 30 days after the last dose of DAA study drug. Events where the onset date is the same as the study drug start date are assumed to be treatment-emergent. If an incomplete onset date was collected for an adverse event, the event will be assumed to be treatment-emergent unless there is other evidence that confirms that the event was not treatment-emergent (e.g., the event end date was prior to the study drug start date).

Adverse event data will be summarized and presented using primary Medical Dictionary for Regulatory Activities (MedDRA) system organ classes (SOCs) and preferred terms (PTs) according to the version of the MedDRA coding dictionary used for the study at the time of database lock. The actual version of the MedDRA coding dictionary used will be noted in the clinical study report. The system organ classes will be presented in alphabetical order and the PT will be presented in alphabetical order within each SOC.

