8.1.6.1 Adverse Events

Adverse events will be coded using the Medical Dictionary for Regulatory Activities (MedDRA).¹² The number and percentage of subjects having DAA treatment-emergent adverse events (i.e., any event that begins or worsens in severity after initiation of study drug through 30 days post-DAA) will be tabulated by primary MedDRA System Organ Class and preferred term. The tabulation of the number of subjects with treatment-emergent adverse events also will be provided with further breakdown by severity rating and relationship to DAA (ABT-450/r or ABT-267), pegIFN, and RBV. Subjects reporting more than 1 adverse event for a given MedDRA preferred term will be counted only once for that term using the most severe incident for the severity rating table and the most related for the relationship to study drug table. Subjects reporting more than

1 type of event within a System Organ Class will be counted only once for that System Organ Class.

The number and percentage of subjects experiencing adverse events with an onset date greater than 30 days post-DAA dosing through 30 days after the last dose of pegIFN/RBV will also be tabulated by primary MedDRA System Organ Class and preferred term.

Additional analyses will be performed if useful and appropriate.

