### **4.0 Study Objectives, Design and Procedures**

#### **4.1 Objectives**

##### **4.1.1 Primary Objective**

The primary objective of this study is to evaluate the safety and antiviral efficacy, defined as the percentage of subjects with sustained virologic response 12 weeks post-dosing (SVR12; HCV RNA < LLOQ 12 weeks after the last dose of study drug), of the study regimen.

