## 4.2 Design Diagram

This is a multicenter, Phase 2, open-label, single-arm, combination treatment study evaluating ABT-450/r in combination with ABT-267, pegIFN and RBV for 24 weeks followed by pegIFN and RBV alone for an additional 24 weeks in HCV genotype 1-infected subjects who have experienced virologic failure while participating in a previous pegIFN-free Abbott/AbbVie DAA combination study. This study consists of a pre-screening period, a screening period and three substudies:

- Substudy 1 (Treatment Intensification [TI]): 24 weeks of therapy with ABT-450/r plus ABT-267 plus pegIFN plus RBV;
- Substudy 2 (pegIFN/RBV [PR] Treatment): 24 weeks of pegIFN and RBV therapy alone;
- Substudy 3 (Post-treatment [PT] Follow-up Period): 48 weeks after last dose of any study drug for resistance monitoring and HCV RNA viral load testing.

A study schematic is shown below (Figure 1).

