### **Adverse Event of Special Interest**

Specific treatment-emergent adverse events of special interest, which may be searched using Standardized, Company or Product MedDRA Queries (SMQs, CMQs, or PMQs), will be summarized. The search criteria for the adverse events of interest are as follows:

- Severe Cutaneous Reactions using the SMQ "Severe cutaneous adverse reactions" (narrow search)

- Hepatic Decompensation and Hepatic Failure (cases identified by the PMQ)
- Hepatocellular carcinoma identified by the following MedDRA preferred terms: hepatocellular carcinoma, hepatic neoplasm, hepatic cancer, and hepatic cancer metastatic

The number and percentage of subjects experiencing at least one treatment-emergent adverse event in the search for the event of interest will be presented by SOC and PT.

A listing of treatment-emergent adverse events for subjects meeting the search criterion will be provided for the adverse event of special interest.

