#### **11.2.2 SAEs (Including Deaths) and Adverse Events Leading to Study Drug Discontinuation**

The number and percent of subjects experiencing treatment-emergent SAEs (including deaths), treatment-emergent adverse events leading to discontinuation of study drug (all study drugs), treatment-emergent adverse events leading to interruption of study drug (all study drugs), treatment-emergent adverse events leading to RBV dose modifications, treatment-emergent adverse events leading to pegIFN dose modifications, and treatment-emergent adverse events leading to death will be tabulated according to the primary SOC and PT.

In addition, the number and percentage of subjects with adverse events leading to RBV dose modifications and adverse events leading to pegIFN dose modifications will be tabulated according to the primary SOC and PT, using adverse events with an onset date greater than 30 days post-DAA dosing through 30 days after the last dose of

pegIFN/RBV. For these summaries, only subjects with the maximum of (last RBV dose date, last pegIFN dose date + 7) greater than DAA Study Drug End Day 1 (e.g., last DAA dose date + 1) will be included.

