### 11.3.2 Statistical Methods

Mean changes from baseline to each post-baseline visit, including applicable post-treatment visits, will be summarized for each protocol-specified laboratory parameter, including IP-10, with the baseline mean, visit mean, change from baseline mean, standard deviation, and median.

Laboratory data values, excluding IP-10, will be categorized as low, normal, or high based on normal ranges of the laboratory used in this study. Shift tables from baseline to minimum value (related to the normal range), maximum value (related to the normal range) and final values during DAA treatment (DAA Study Drug End Day  $\leq 2$ ) will be created. The shift tables cross tabulate the frequency of subjects with baseline values below/within/above the normal range versus minimum/maximum/final values below/within/above the normal range. The shift tables will also cross tabulate the frequency and percentage of subjects with baseline values below/within the normal range versus minimum/maximum/final values below/within/above the normal range. The shift tables will also cross tabulate the frequency and percentage of subjects with baseline values within/above the normal range versus minimum/maximum/final values below/within/above the normal range.

Frequencies and percentages of subjects with post-baseline chemistry and hematology values during DAA treatment (DAA Study Drug End Day  $\leq$  2) meeting criteria for Potentially Clinically Significant (PCS) Laboratory Values (Table 5 and Table 6) will be summarized. A post-baseline value must be more extreme than the baseline value to be considered as a PCS finding. Listings will be provided that presents all of the subjects and values meeting the PCS criteria (at any time during the study).

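### The SAP drops, unlogged, the protocol's table of adverse events arising after the DAA period, and stops laboratory abnormality counts at the end of DAA dosing

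*SAP*

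**What the plan says.** **Adverse events, protocol.** Protocol 8.1.6.1 plans two tabulations by system organ class (SOC) and preferred term (PT). The first covers events that begin or worsen from first dose to 30 days after the last DAA dose. The second is plain: "adverse events with an onset date greater than 30 days post-DAA dosing through 30 days after the last dose of pegIFN/RBV will also be tabulated", again by SOC and PT, with no restriction on the type of event.

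**Adverse events, SAP.** SAP 11.2.1 keeps the first window as its default: "summaries of adverse events will include adverse events that are treatment-emergent relative to dosing of the DAAs". SAP 11.2.2 is the only place that tabulates events from the second window, and it does so for one subset: "the number and percentage of subjects with adverse events leading to RBV dose modifications and adverse events leading to pegIFN dose modifications will be tabulated". In SAP 11.2.3 every listing is confined to treatment-emergent events, except the listing of all serious adverse events from consent to end of study.

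**Laboratory data.** Protocol 8.1.6.2 plans shift, PCS and maximum-grade summaries on post-baseline values and sets no cut at the end of DAA dosing. SAP 11.3.2 confines all three to DAA Study Drug End Day 2 or earlier. The PCS summary, for instance, is of "Frequencies and percentages of subjects with post-baseline chemistry and hematology values during DAA treatment" that meet the criteria.

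**Change log.** SAP 12.1.1 lists eight differences from the protocol. None concerns adverse event or laboratory analyses.

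**The concern.** SAP 4.1.1 states: "The primary objective of this study is to evaluate the safety and antiviral efficacy" of the study regimen. That regimen is 48 weeks long, and the protocol's definition of terms names pegIFN and RBV as the Substudy 2 study drugs. Protocol 6.4 collects all adverse events until 30 days after the last dose, pegIFN and RBV included. The data will therefore exist, but most of the later part has no planned incidence summary.

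The loss falls on three kinds of result:

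- **Late non-serious adverse events without dose modification.** These appear in no specified table or listing, even if severe.
- **Late serious events and events leading to discontinuation.** These have no SOC/PT incidence table for the later window, although serious events are listed and discontinuations are counted by reason.
- **Laboratory abnormalities in Substudy 2.** Protocol 3.2 names cytopenias among the known toxicities of pegIFN and RBV. Neutrophils and platelets are not in the SAP's grade table (SAP Table 7), so the PCS and shift tables are their only abnormality counts, and both stop with the DAAs.

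Protocol 5.6.1 also says that safety will be compared with historical data for pegIFN and RBV, a therapy that Protocol 3.0 describes as lasting up to 48 weeks. Incidence counted over roughly the first half of treatment is a poor match for that comparison.

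**Working it through.** **Inputs**

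- Substudy 1: "24 weeks of therapy with ABT-450/r plus ABT-267 plus pegIFN plus RBV" (SAP 4.2), so 24 × 7 = 168 days.
- Substudy 2: "24 weeks of pegIFN and RBV therapy alone" (SAP 4.2), a further 168 days.
- Post-treatment follow-up: 48 weeks (SAP 4.2).
- Adverse event window: last DAA dose + 30 days (SAP 11.2.1).
- Laboratory count window: last DAA dose + 2 days (SAP 11.3.2).
- Adverse event collection: last dose of any study drug + 30 days (Protocol 6.4).

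**The plan's own figure.** 24 + 24 + 48 = 96 weeks, the study duration given in SAP 4.2. Treatment is 24 + 24 = 48 weeks = 336 days.

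**Completer, adverse events**

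- The window closes on day 168 + 30 = 198.
- Dosing days outside it: 336 − 198 = 138; 138/336 = 41%; 138/7 = 19.7 weeks.
- The omitted protocol table would run from day 198 to day 336 + 30 = 366, which is 168 days (24.0 weeks): those 138 dosing days plus 30 days after dosing.

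**Completer, laboratory abnormality counts**

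- The window closes on day 168 + 2 = 170.
- Dosing days outside it: 336 − 170 = 166; 166/336 = 49%; 166/7 = 23.7 weeks.

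**Subjects who stop DAAs early and take pegIFN/RBV to 48 weeks in total.** Protocol 5.1.3 allows this at the investigator's discretion, and Protocol 5.4.1.1 provides for it at TI Week 4. The stopping weeks below are illustrative.

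| DAA stop | Dosing days outside AE window | Dosing days outside lab window |
|---|---|---|
| Week 4 | 336 − (28 + 30) = 278 (83%, 39.7 weeks) | 336 − (28 + 2) = 306 (91%, 43.7 weeks) |
| Week 12 | 336 − (84 + 30) = 222 (66%, 31.7 weeks) | 336 − (84 + 2) = 250 (74%, 35.7 weeks) |
| Week 24 | 336 − (168 + 30) = 138 (41%, 19.7 weeks) | 336 − (168 + 2) = 166 (49%, 23.7 weeks) |

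**What the SAP still reports after the DAA period**

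| Output | Reaches Substudy 2 or later? | Place in SAP |
|---|---|---|
| AEs leading to RBV or pegIFN dose modification, by SOC/PT | Yes | 11.2.2 |
| Listing of all serious AEs | Yes, to end of study | 11.2.3 |
| Study drug discontinuation by reason | Yes, Substudies 1 and 2 | 8.0 |
| Mean laboratory change by visit | Yes | 11.3.2 |
| Listing of PCS laboratory values | Yes, any time | 11.3.2 |
| Vital signs by visit, listing of PCS vital signs | Yes | 11.4.2 |
| All AEs by SOC/PT | No | 11.2.1 |
| Laboratory shift, PCS and grade counts | No | 11.3.2 |

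**The case against.** A reader might infer that the DAA-based definition of treatment-emergent is itself the departure. It is not: Protocol 8.1.6.1 defines the window the same way. The fault is the loss of the companion table.

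A reader might also infer that the SAP removed a whole family of late tables, covering severe, drug-related, discontinuation and special-interest events. The protocol never planned these for the later window; it asked for one plain SOC/PT table. That the SAP summarizes "Specific treatment-emergent adverse events of special interest", and not later ones, contradicts nothing in the protocol.

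Nor do the documents support the claim that post-DAA safety goes unreported. The table under working shows six kinds of output that reach Substudy 2. With up to 35 subjects (protocol synopsis), the listings of serious events and PCS values will show late serious events and laboratory extremes directly.

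Finally, the sponsor can say that the study is descriptive, that the uncovered weeks are pegIFN and RBV alone, whose safety Protocol 5.6.4 regards as well characterized, and that no data are lost because the tables can be run later. This limits the harm, and primary efficacy is untouched. It does not explain why a planned table disappeared without a note. The protocol asked for it knowing what pegIFN and RBV do, and Protocol 3.2 says that these four agents had not been dosed together before. If the sponsor now thinks the table unnecessary, Section 12 is the place to say so.

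**Conclusion.** The point holds in a limited form. One protocol-specified adverse event table is missing from the SAP, and laboratory shift, PCS and grade counts carry a cut-off that the protocol does not set. Neither change is logged. For a completer the gap is 138 of 336 dosing days (41%) for general adverse event incidence and 166 of 336 (49%) for laboratory abnormality counts; both gaps widen when DAAs stop early and pegIFN/RBV continues.

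These figures assume that DAAs end on day 168 and pegIFN/RBV on day 336. The early-stop figures show what can happen to one subject, since the documents do not say how many will follow that path. The figures measure uncovered time, not missed events. A reader might infer that the reported toxicity will be understated by a similar fraction, but the documents give no expected late event rate, so that size cannot be stated. What can be said is that incidence from the planned tables describes the DAA period and should not be read as incidence over the 48-week regimen.

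**What to change.** - **SAP 11.2:** reinstate the protocol's SOC/PT table of all adverse events with onset more than 30 days after the last DAA dose, through 30 days after the last pegIFN/RBV dose. SAP 11.2.2 already defines this window and a denominator for its dose-modification tables, so both can be reused.
- **SAP 11.3.2:** run the laboratory shift, PCS and grade tables through the end of pegIFN/RBV, and keep the DAA-period versions as a separate view.
- **SAP Section 12:** list and justify any departure from Protocol 8.1.6.1 or 8.1.6.2 that remains.
- **Optional, beyond the protocol:** whole-regimen tables (first dose to 30 days after the last dose of any study drug) for the overview, severe events, events leading to discontinuation, and events of special interest.

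The cost is SAP wording and reruns of existing table programs on data already collected. The report gains a few tables and will show higher event rates than the DAA-period tables alone. The changes are best made before the database is locked.

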### **Adverse Event Overview**

An overview of adverse events will be presented consisting of the number and percentage of subjects experiencing at least one event for each of the following adverse event categories:

- Treatment-emergent adverse events
- Treatment-emergent adverse events possibly or probably related to DAAs
- Treatment-emergent adverse events possibly or probably related to pegIFN
- Treatment-emergent adverse events possibly or probably related to RBV
- Treatment-emergent severe adverse events
- Treatment-emergent serious adverse events
- Treatment-emergent adverse events leading to study drug (all study drugs) discontinuation
- Treatment-emergent adverse events leading to interruption of study drug (all study drugs)
- Treatment-emergent adverse events leading to RBV dose modifications
- Treatment-emergent adverse events leading to pegIFN dose modifications
- Treatment-emergent adverse events leading to death

- Deaths

### **Adverse Event by SOC and PT**

For each of the following events, the number and percentage of subjects experiencing treatment-emergent events will be tabulated by SOC and preferred term (PT):

- Treatment-emergent adverse events
- Treatment-emergent adverse events possibly or probably related to DAAs
- Treatment-emergent adverse events possibly or probably related to pegIFN
- Treatment-emergent adverse events possibly or probably related to RBV
- Severe treatment-emergent adverse events

Subjects reporting more than one adverse event for a given PT will be counted only once for that term (most related incident for the relationship tables and most severe incident for the severity tables). Subjects reporting more than one type of adverse event within a SOC will be counted only once for that SOC. Subjects reporting more than one type of adverse event will be counted only once in the overall total.

### **Adverse Events by PT**

The number and percentage of subjects experiencing treatment-emergent adverse events will be tabulated according to preferred term and sorted by overall frequency. A similar summary will be provided for treatment-emergent adverse events possibly or probably related to DAAs.

### **Adverse Event of Special Interest**

Specific treatment-emergent adverse events of special interest, which may be searched using Standardized, Company or Product MedDRA Queries (SMQs, CMQs, or PMQs), will be summarized. The search criteria for the adverse events of interest are as follows:

- Severe Cutaneous Reactions using the SMQ "Severe cutaneous adverse reactions" (narrow search)

- Hepatic Decompensation and Hepatic Failure (cases identified by the PMQ)
- Hepatocellular carcinoma identified by the following MedDRA preferred terms: hepatocellular carcinoma, hepatic neoplasm, hepatic cancer, and hepatic cancer metastatic

The number and percentage of subjects experiencing at least one treatment-emergent adverse event in the search for the event of interest will be presented by SOC and PT.

A listing of treatment-emergent adverse events for subjects meeting the search criterion will be provided for the adverse event of special interest.

#### **Adverse Events by Maximum Severity**

Treatment-emergent adverse events will also be summarized by maximum severity of each preferred term. A similar summary will be provided for treatment-emergent adverse events possibly or probably related to DAAs. If a subject has an adverse event with unknown severity, then the subject will be counted in the severity category of "unknown," even if the subject has another occurrence of the same event with a severity present. The only exception is if the subject has another occurrence of the same adverse event with the most extreme severity, "Severe." In this case, the subject will be counted under the "Severe" category.

#### **Adverse Events by Maximum Severity Grade Level**

Treatment-emergent adverse events will be summarized by maximum severity grade level of each preferred term. Each preferred term will be assigned a grade level based on severity and seriousness, adapted from the Division of AIDS (DAIDS) table for grading severity of adverse events. All serious adverse events will be categorized as Grade 4. Non-serious adverse events categorized by the investigators as mild, moderate or severe will be categorized as Grade 1, Grade 2, or Grade 3, respectively. If a subject has a non-serious adverse event with unknown severity, then the subject will be counted in the severity grade level category of "unknown," even if the subject has another occurrence of the same event with a severity present. The only exception is if the subject has another

occurrence of the same adverse event with the most extreme severity – "Severe." In this case, the subject will be counted under the "Grade 3" category. Similarly, if a subject has an adverse event with unknown seriousness, then the subject will be counted in the severity grade level category of "unknown" unless the subject has another occurrence of the same adverse event that is marked serious. In this case, the subject will be counted under the "Grade 4" category.

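### The unknown-severity rule in the adverse event grade table conflicts with the SAP's own Grade 4 rule for serious events, so a term's Grade 4 count can be one too low per affected subject

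*SAP*

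**What the plan says.** The rules are in SAP 11.2.1, under Adverse Events by Maximum Severity Grade Level.

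- **What is reported.** "Treatment-emergent adverse events will be summarized by maximum severity grade level of each preferred term".
- **Serious events.** "All serious adverse events will be categorized as Grade 4".
- **Non-serious events.** "Non-serious adverse events categorized by the investigators as mild, moderate or severe will be categorized as Grade 1, Grade 2, or Grade 3, respectively".
- **Unknown severity.** A subject with a non-serious event of unknown severity goes to the unknown category, "even if the subject has another occurrence of the same event with a severity present". One exception is named, and it is described as the only one: another occurrence of the term is rated Severe, in which case "the subject will be counted under the 'Grade 3' category".
- **Unknown seriousness.** A subject with an event of unknown seriousness also goes to unknown, "unless the subject has another occurrence of the same adverse event that is marked serious"; the subject is then Grade 4.

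Two neighbouring parts of 11.2.1 matter. The general counting rule for repeated terms uses the "most severe incident for the severity tables". The three-level severity table (Adverse Events by Maximum Severity) has the same unknown-severity exception, but there Severe is the highest category.

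**The concern.** On the grade scale of this table, a non-serious event of unknown severity can be at most Grade 3. If the same subject also has a serious occurrence of the term, the maximum is Grade 4 whatever the missing severity would have been, so nothing is left for an unknown category to represent. The unknown-severity rule nevertheless gives unknown or Grade 3, because its sole exception looks for a severe occurrence and never for a serious one. In the three-level table that exception is complete. In a four-level table with a category above Severe, it is not.

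The companion rule for unknown seriousness does let a serious occurrence prevail. The two rules therefore treat a serious occurrence differently with no stated reason.

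At stake is agreement between tables. An affected subject would appear in the serious adverse event table for a preferred term and be missing from the Grade 4 row for that term.

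**Working it through.** The plan gives no figure on this point, so there is none to reproduce. The check applies the written rules to each possible pair of occurrences and compares the result with the maximum event-level grade.

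**Inputs (all SAP 11.2.1).** Seriousness: yes, no or unknown. Severity: mild, moderate, severe or unknown. Serious = Grade 4; non-serious mild, moderate, severe = Grades 1, 2, 3.

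**Step 1: number of pairs.** There are 3 × 4 = 12 kinds of occurrence. Unordered pairs, repeats allowed: 12 × 13 / 2 = 78. Pairs with no serious occurrence use the other 8 kinds: 8 × 9 / 2 = 36. Pairs with at least one serious occurrence: 78 − 36 = 42.

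**Step 2: pairs misplaced by the literal unknown-severity rule.** The rule is triggered only by a non-serious occurrence of unknown severity. Paired with a serious occurrence, that leaves four cases:

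| Serious occurrence is | Literal rule gives | Maximum event-level grade |
|---|---|---|
| mild | unknown | 4 |
| moderate | unknown | 4 |
| of unknown severity | unknown | 4 |
| severe | Grade 3 | 4 |

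So 4 of the 42 pairs are misplaced. These are kinds of pair, not expected frequencies.

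**Step 3: effect on the counts.** In all four cases the Grade 4 count for the term is low by 1. In the first three, the unknown count is high by 1. In the fourth, the Grade 3 count is high by 1, so a count of Grade 3 or above would be unchanged.

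**Step 4: a third occurrence of unknown seriousness.** Both rules now apply. With a serious mild occurrence, the severity rule gives unknown and the seriousness rule gives Grade 4. With a serious severe occurrence, they give Grade 3 and Grade 4. The text does not say which rule prevails.

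**Step 5: scale.** The protocol synopsis plans up to 35 subjects but also says that enrolment has no lower or upper limit, and SAP 4.3 sets no sample size. N is therefore an assumption:

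- N = 35: 1/35 = 2.86%, about 2.9 percentage points per affected subject and term.
- N = 20 (illustrative): 1/20 = 5.0 percentage points.

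**The case against.** The strongest reply is that the text can be read correctly. The Grade 4 sentence for serious events is unconditional, the table reports a maximum, the disputed rule is triggered only by a non-serious event, and the next rule lets a serious occurrence prevail. A programmer could reasonably code Grade 4 from this. That stands in part: it shows what was probably intended, and it means that the wrong count is not certain. It does not remove the conflict. Calling the severe case the only exception is explicit, and a programmer who follows it literally gets a different table from one who follows the Grade 4 sentence.

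The reply is also right that the trigger is narrow. One subject must have two occurrences of the same preferred term, one serious and one non-serious with severity missing. Protocol 6.0 requires severity to be recorded, 6.2 supplies the scale, and 10.2 provides for review of the eCRFs for completeness. Nothing in the documents suggests that the pattern will be common.

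Three stronger readings are tempting, and the documents do not support them.

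- **Counts of Grade 3 or above are too low.** In the serious-and-severe case such a count does not change. The SAP also specifies no such row for this table; the rows for at least Grade 3 in SAP 11.3.2 concern laboratory values.
- **Serious events drop out of the report.** They are counted in the overview (11.2.1), tabulated by system organ class and preferred term (11.2.2) and listed (11.2.3), none of which uses the grade rule.
- **A severe event of unknown seriousness is wrongly labelled unknown.** It could be Grade 3 or Grade 4, so unknown is a defensible label, and forcing it to Grade 3 could under-grade it.

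**Conclusion.** The point holds as a conflict within one SAP subsection. Applied literally, the unknown-severity rule gives a result that contradicts both the Grade 4 rule for serious events and the reporting of a maximum. The Grade 4 count for a preferred term can be too low by one per affected subject, about 2.9 percentage points if N = 35 and more if fewer subjects are treated.

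This rests on two conditions: the programmer follows the stated exception rather than the Grade 4 sentence, and at least one subject has the triggering pair of occurrences. The documents settle neither, and the number affected may be zero. The consequence is confined to one descriptive safety table. It is a minor correction, worth making because the rule as written can give a wrong count and the repair is almost free.

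**What to change.** In SAP 11.2.1, Adverse Events by Maximum Severity Grade Level, insert one precedence sentence before both unknown rules:

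> A subject with any serious occurrence of the preferred term is counted as Grade 4; the rules for unknown severity and unknown seriousness apply only to subjects with no serious occurrence of that term.

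Placing it ahead of both rules also removes the contradiction found in step 4. The Grade 4 clause in the unknown-seriousness rule then becomes redundant and may stay or go. The labelling of a severe event with unknown seriousness should be left alone.

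The cost is one sentence in the SAP and one line of program logic, with no new data and no change to any other table.
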